**Statistical Characteristics of the Two Stage Design**

If the regimen is associated with a true response rate of 45%, which is approximately the maximum likelihood estimate of the response rate associated with VI, the design will identify the regimen as not sufficiently effective for further development with probability 0.90. If the regimen is associated with a true response rate of 65%, the regimen will be considered of sufficient efficacy to warrant further development with probability 0.90. The probability enrollment will be terminated at the first stage of accrual if the true response rate is 45% is 0.435.

The response status used for the application of the statistical rule will be that obtained from the central review of RECIST response and the alphafetoprotein values and sampling dates provided by the institutional investigator. If there is a discrepancy between the assessment by central review and by institutional assessment, the study PI will discuss with the treating physician to resolve the discrepancy.

If the investigator selects a post-induction regimen that is *not* indicated by the central review of response, the patient will be considered off protocol therapy as of the start date of consolidation therapy.

Hypothesis 2.0: Referral Feasibility:

All patients enrolled on the planned COG phase III study of hepatoblastoma (AHEP0731) and who have Stage III or IV disease and whose tumor is PRETEXT classified as PRETEXT 3-4 extensive multifocal;

PRETEXT 3 +V; PRETEXT 3 +P; or PRETEXT 4 extensive multifocal will be evaluable for this portion of the study ('referable extent of disease'). A recent retrospective analysis of the data from INT-0098 looked at the PRETEXT grouping of tumors in patients with Stage III and Stage IV disease. In the years since INT-0098 the PRETEXT system has been increasingly employed by the European SIOPEL studies of pediatric hepatoblastoma in an attempt to define resectability.

INT-0098 was a POG/CCG cooperative trial enrolling 182 children with hepatoblastoma in the early 1990's. In our retrospective review, detailed surgical and pathology reports enabling accurate retrospective PRETEXT grouping were available for 155 of the initial 182 patients. By the proposed definition of resectability in this study, INT-0098 included 32 patients with potentially unresectable tumors who might have been referred early for potential transplantation. The precise breakdown from INT-0098 is as follows:

Stage III: PRETEXT 2 multifocal = 1  
 PRETEXT 3 multifocal or +V or +P = 8  
 PRETEXT 4 = 13  
 Stage IV: PRETEXT 2 multifocal = 0  
 PRETEXT 3 multifocal or +V or +P = 2  
 PRETEXT 4 = 8  
 Total = 32

INT-0098 was open for enrollment for 4 years. As a conservative estimate, using the 32 patients as the projected number of patients for whom referral is appropriate, we expect referral will be appropriate for approximately 25 patients enrolled to AHEP0731.

Patients enrolled on this study will be considered candidates for referral provided the patient has a referable stage of disease and receives two cycles of chemotherapy and is still considered on protocol therapy at the end of the second cycle. A patient will be considered a referral success if: (1) the patient is enrolled on regimen F or regimen H and referred for transplant prior to the start of the third cycle of chemotherapy; or (2) the patient is enrolled on regimen H or W and is referred for transplant by the start of the third cycle of C5VD. Otherwise the patient will be considered a referral failure. In particular, a patient who has a referable stage of disease, is treated on regimen H or W and has protocol therapy terminated after the completion of cycle 2 but before the completion of cycle 4 without being referred for transplant will be considered a referral failure.

The feasibility of referral will be evaluated for each of the expected 25 patients who would be amenable to OLT. A patient for whom referral is considered appropriate who receives a consultation after enrollment will be considered a success with respect to feasibility. If referral is accomplished for 16 or more patients, the strategy will be considered successful and identified for possible incorporation into a randomized study. The characteristics of this rule as a function of the true 'success' probability are:

True Probability of Successful Referral	Chance Referral Will be Identified as Feasible
0.50	11%
0.55	24%
0.60	42%
0.65	63%
0.70	81%
0.75	93%

If more than 25 patients are identified as candidates for referral, the number of patients for whom referral

is accomplished required to consider referral “feasible” will be increased in such a way as to yield “Chance Referral Will be Identified as Feasible” probabilities of greater than 80% for the scenarios identified by the last two lines in the table above.

All patients who are referred for OLT evaluation and considered candidates for such a surgery will contribute to the evaluation of secondary aim 1.3.2. If we conclude referral is feasible, we estimated conservatively 16 patients would be referred. We estimate that 2 such patients will not be candidates for OLT because of technical reasons. If 8 or more of the 14 patients considered candidates for OLT receive such a procedure, OLT will be considered a candidate for possible incorporation into a randomized trial. The characteristics of this rule as a function of the true ‘success’ probability is:

Probability of OLT Performed on a Potential Candidate	Chance OLT will be Identified for Possible Incorporation Into a Randomized Trial
0.50	0.40
0.55	0.55
0.60	0.69
0.65	0.82
0.70	0.90
0.75	0.96

If more than 14 patients are successfully referred for OLT the current cutoff of 8 noted in the paragraph above will be increased in a manner similar to that described for the analysis of feasibility of referral.

Any patient from this secondary endpoint analysis population that receives an OLT will be considered a success with respect to the secondary aim 1.3.3. All patients in this cohort will be further subdivided into one of four outcome-of-transplant attempt groups: (a) proven to be resectable with a conventional surgery; (b) remain unresectable, primary transplant performed after a good initial response to chemotherapy; (c) remain unresectable, no surgery performed due to persistent metastatic disease unresponsive to chemotherapy or surgical resection; or (d) do not proceed to surgery because of refusal or deteriorating patient condition.

Two years after the last patient is enrolled we will calculate the 95% confidence interval for the 2-year EFS. If OLT is considered for possible incorporation into a randomized trial, we estimate conservatively that 8 patients will have undergone an OLT. The expected width of the 95% confidence interval is:

Expected 95% Confidence Interval Widths as a Function of the True 2-Year EFS

True 2-Year EFS	Expected 95% Confidence Interval for 2-Year EFS
0.50	0.17-0.83
0.60	0.24-0.88
0.70	0.32-0.93
0.80	0.42-0.97
0.90	0.54-0.99

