- PRETEXT 3 extensive multifocal;
- PRETEXT 3 +V;
- PRETEXT 3 +P; or
- PRETEXT 4 extensive multifocal

Recent studies have shown long-term survival and cure in patients with known microscopic residual disease. For example, SIOPEL-1 evidenced that microscopic margins had no effect on the rate of survival. The implications of microscopic margins are thus poorly understood and have never been evaluated prospectively in any hepatoblastoma trial. Microscopic positive margins have been repeatedly shown to increase the risk of local relapse, metastatic relapse, and death in patients with hepatocellular carcinoma. However, the implications of microscopically-positive margins on the recurrence and survival of patients with hepatoblastoma remains unclear. Data to be collected for AHEP0731 will allow exploration of this issue.

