#### 13.1.3 Tumors With Potential Need for Liver Transplant or Extreme Resection

- Definition of potential candidate for liver transplant or extreme resection based upon radiographic imaging obtained at diagnosis (PRETEXT) and after the SECOND cycle of C5VD chemotherapy (POST-TEXT):
  - Major Venous Invasion: Unifocal PRETEXT/POST-TEXT 3 with tumor ingrowth of all 3 hepatic veins or the retrohepatic vena cava (+V), or portal vein or both right and left (+P). The distinction between major venous “ingrowth” by tumor vs major venous “displacement” or “extrinsic compression” by tumor can be radiographically very difficult. Clinicians are encouraged to err on the side of “possible invasion” and refer patient for transplant evaluation if this distinction is very difficult to make.

- Unifocal PRETEXT/POST-TEXT 4
- Multifocal PRETEXT/POST-TEXT 3 and 4
- **Refer to surgical center with expertise in pediatric liver transplant and “extreme” liver resection at diagnosis if possible and no later than the first day of the 3rd cycle of C5VD neoadjuvant chemotherapy.** Resection planning is to be completed before completion of the 4th cycle of chemotherapy. Transplant or “extreme” resection is to occur within 4 weeks of completing the 4th cycle of chemotherapy.

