## Biopsy and Refer at Diagnosis

Tumor expected to require liver transplantation or extreme, complex liver resection

- multifocal PRETEXT 3 or 4
- PRETEXT 3 +V, +P
- PRETEXT 4

Consultation with liver program to complete transplant evaluation and listing with goal of transplant on or before completion of four cycles neoadjuvant chemotherapy

AHEP 0731 Surgical Resection Guidelines

**Biopsy at Diagnosis  
Neoadjuvant Chemotherapy**

[figure not shown]
**POST-TEXT => Repeat CT Scan  
after 2nd cycle chemotherapy**

- \* Resect after 2nd cycle chemo
  - POST-TEXT 1
  - POST-TEXT 2 if there is > 1cm radiographic margin on middle hepatic vein and portal bifurcation
- \*\* Resect after 4th cycle chemo
  - POST-TEXT 2 < 1 cm margin
  - POST-TEXT 3

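### The population scored for referral aim 1.2.4 leaves out unifocal PRETEXT 4 tumors, which the surgical guidelines send for referral and the planning count includes

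*Combined protocol and SAP*

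**What the plan says.** Aim 1.2.4 sets a 70% target for timely consultation among patients whose tumors may prove unresectable. It puts no limit on focality.

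**Analysis population.** Section 9.2, Hypothesis 2.0, evaluates Stage III or IV patients "whose tumor is PRETEXT classified as PRETEXT 3-4 extensive multifocal", and goes on to say that "PRETEXT 3 +V; PRETEXT 3 +P; or PRETEXT 4 extensive multifocal will be evaluable for this portion of the study". Section 2.5 gives the same groups as its definition of potential need for transplant, ending with "PRETEXT 4 extensive multifocal". Neither list admits a PRETEXT 4 tumor that is a single focus.

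**Referral guidance.** Section 13.1.3 has separate entries for "Unifocal PRETEXT/POST-TEXT 4" and "Multifocal PRETEXT/POST-TEXT 3 and 4", the latter without the word extensive. The instruction that follows begins "Refer to surgical center with expertise in pediatric liver transplant and". The Appendix I page on referral at diagnosis carries the description "Tumor expected to require liver transplantation or extreme, complex liver resection". It lists multifocal PRETEXT 3 or 4, PRETEXT 3 with +V or +P, and, on a line of its own, PRETEXT 4 with no qualifier.

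**Planning count.** Section 9.2 states: "By the proposed definition of resectability in this study, INT-0098 included 32 patients with potentially unresectable tumors". From this it expects about 25 candidates in AHEP0731 and calls referral feasible if 16 or more succeed. The cut-off is to be raised if there are more than 25 candidates. No rule is given for fewer.

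**The concern.** Three populations ought to coincide: the patients sites are told to refer, the patients used to size the rule, and the patients scored. The first two take PRETEXT 4 of any focality. The third takes only extensive multifocal PRETEXT 4.

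Under Section 9.2 as written, a child with a unifocal PRETEXT 4 tumor who should be referred under Section 13.1.3 and is missed does not count as a failure. One who is referred does not count as a success. This holds even with +V or +P, although a PRETEXT 3 tumor with +V or +P is scored. The effect on the observed proportion could go either way.

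The result decides whether referral is put forward for a randomized study, and the planning for aims 1.3.2 and 1.3.3 is built on it (16 referred, 14 transplant candidates, 8 transplanted).

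**Working it through.** **1. The plan's own figures.** With X the number of successful referrals among n = 25 candidates, the chance of passing is P(X ≥ 16) = Σ C(25,k) p^k (1−p)^(25−k), summed over k = 16 to 25.

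| True rate p | Section 9.2 | Recomputed |
|---|---|---|
| 0.50 | 11% | 11.5% |
| 0.55 | 24% | 24.2% |
| 0.60 | 42% | 42.5% |
| 0.65 | 63% | 63.0% |
| 0.70 | 81% | 81.1% |
| 0.75 | 93% | 92.9% |

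All six entries reproduce. The fault lies in the population, not in the arithmetic.

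**2. The INT-0098 count (Section 9.2).** Stage III: 1 multifocal PRETEXT 2, 8 PRETEXT 3 (multifocal, +V or +P), 13 PRETEXT 4. Stage IV: 0, 2 and 8. The sum 1 + 8 + 13 + 0 + 2 + 8 = 32 is right. PRETEXT 2 and 3 carry a qualifier in that breakdown; PRETEXT 4 carries none.

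- PRETEXT 4 of any focality: 13 + 8 = 21, and 21/32 = 66%.
- On the Section 13.1.3 or Appendix I list: 10 + 21 = 31. The multifocal PRETEXT 2 case is on no list.
- On the Section 9.2 list: 10 + 21m, where m is the share of PRETEXT 4 that is extensive multifocal. The documents do not give m. This also assumes that all ten PRETEXT 3 cases meet the narrow list, although the breakdown does not say extensive.

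**3. Expected candidates, scaling the planned 25.** Multiply by 25/32.

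| m | INT-0098 count | Expected candidates |
|---|---|---|
| 0 | 10 | 7.8 |
| 0.25 | 15.25 | 11.9 |
| 0.50 | 20.5 | 16.0 |
| 0.75 | 25.75 | 20.1 |
| 1 | 31 | 24.2 |

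The last row is also the count with every PRETEXT 4 tumor included. At 24.2 it is close to the planned 25, so the rule was in effect sized for the broad population.

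**4. Expected candidates, scaling to apparent enrolment.** INT-0098 had 83 Stage III and 40 Stage IV patients, 123 in all (Section 2.3.3). Here stratum 3 enrolled 105 (Section 9.2), the Regimen W cohort was 30 (Section 2.3.4), and Regimen H takes 22 to 43 (Section 9.2). The total is 157 to 178. Expected candidates are (10 + 21m)/123 × 157 to 178:

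- m = 0.25 (75% not extensive multifocal): 15.25/123, giving 19.5 to 22.1
- m = 0.50: 20.5/123, giving 26.2 to 29.7
- m = 0.75: 25.75/123, giving 32.9 to 37.3

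This is rough. Strata 3 and 4 hold some patients who are not Stage III or IV, and some will not complete two cycles. In the other direction, only 155 of the 182 INT-0098 patients could be PRETEXT-grouped, so dividing by 123 understates the candidate rate.

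**5. The rule if candidates fall below 25.** With the cut-off held at 16 and p = 0.70, the chance of passing is 0.81 at n = 25, 0.73 at n = 24, 0.24 at n = 20 and 0.003 at n = 16. Below 16 candidates it cannot be met.

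**The case against.** The narrow list is not an isolated slip. Section 2.5 carries it too, and an analysis population may be narrower than a clinical guideline. Everyone on the Section 9.2 list is also referable under Section 13.1.3, so a reader who infers that the rule is applied to the wrong patients goes too far: they are an incomplete subset. Section 9.2 names extensive multifocal PRETEXT 4 twice, but that repetition changes nobody's classification.

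A reader might also infer that the chance of passing drops from 0.81 to 0.24. The documents do not show this. The plan calls its 25 conservative, and on apparent enrolment the narrow population exceeds 25 at unifocal shares of 25% and 50%. There Section 9.2 raises the cut-off so as to keep the chance above 80% at true rates of 0.70 and 0.75.

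Nor does it follow that the trial cannot judge its own referral guidance. Multifocal PRETEXT 4 patients are scored. PRETEXT grouping and transplant consultation are on the required schedules for strata 3 and 4 (Sections 7.4 and 7.5), so unifocal cases can at least be described.

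These points limit the size of the problem. They do not remove it. A deliberate restriction would not explain why the planning count, said to follow this study's definition, takes PRETEXT 4 without qualifier. The documents contain two definitions and do not say which one governs the aim.

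**Conclusion.** The concern holds as a mismatch of populations. Sections 9.2 and 2.5 exclude unifocal PRETEXT 4 from the scored group. Section 13.1.3, Appendix I and the planning count include it. PRETEXT 4 is 21 of the 32 planning patients, so the group affected is potentially large, but its unifocal part is not stated.

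The effect on numbers is a range: about 8 to 24 candidates if the 25 is scaled, and about 19 to 37 if apparent enrolment is used with unifocal shares of 75% to 25%. Both rest on assumed shares and on INT-0098 proportions carrying over. The loss of power is conditional: it arises only if candidates fall below 25 while the cut-off stays at 16. The mismatch itself depends on none of these assumptions.

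**What to change.** Reconcile Sections 2.5, 9.2, 13.1.3 and Appendix I. Which tumors ought clinically to be referred is not a matter for this review.

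For the analysis only:

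- Define the Section 9.2 evaluable population by PRETEXT at diagnosis, so that it matches the tumors sites were instructed to refer and the planning count: PRETEXT 3 with +V or +P, any multifocal PRETEXT 3 or 4, and any PRETEXT 4, unifocal included. Section 13.1.3 also uses imaging after the second C5VD cycle; grouping at diagnosis keeps the denominator independent of response to chemotherapy.
- Restate the INT-0098 count under that definition as 31, not 32.
- Report the referral proportion under the current narrow list as a sensitivity analysis.
- Fix and document the definition before referral outcomes are examined. Accrual has closed, and a denominator chosen with the results in view would be open to challenge.

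The cost is wording in Sections 9.2 and 2.5 and one re-tabulation, since PRETEXT grouping is already collected and centrally reviewed. The downside is that the denominator of a primary aim changes and the observed rate may be less favourable.

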## ABSTRACT

Hepatoblastoma is the most common malignant liver neoplasm in children. Although surgical resection is the mainstay of curative therapy for children with hepatoblastoma, only one-third to one-half of newly diagnosed patients with hepatoblastoma can be expected to have resectable disease at presentation. Patients who undergo a primary complete resection of their tumor have an excellent prognosis (90% event-free survival [EFS]). The use of chemotherapy has improved survival in patients with unresectable hepatoblastoma by increasing the number of patients whose tumors can be resected. However, more recent trials over the last decade have failed to significantly improve survival numbers. Therefore, the current EFS for the entire group of patients with non-metastatic, unresectable hepatoblastoma at diagnosis remains suboptimal (< 70%) and warrants novel treatment approaches. The survival of patients with metastatic disease at diagnosis remains poor (20-30%) and also requires consideration of novel therapeutic strategies. AHEP0731 builds on the results of the last 20 years of hepatoblastoma clinical trials and seeks to diminish toxicity in the approximately 30% of low-risk patients, increase survival in intermediate-risk patients and identify new agents(s) that may be used in high-risk and recurrent patients. Patients will be staged for risk classification and treatment at diagnosis using COG staging guidelines (see [Appendix III](#)). Study enrollment for patients with Stage I and II tumors is contingent on rapid central pathologic review of tumor specimens. All patients with Stage I pure fetal histology (PFH) hepatoblastoma will be classified as very low-risk and will be treated with surgery only. Patients with Stage I non-PFH, non-small cell undifferentiated (SCU) hepatoblastoma or with Stage II non-SCU hepatoblastoma will be classified as low-risk and will be treated on Regimen T with 2 adjuvant cycles of cisplatin, 5-fluorouracil, and vincristine (C5V), a reduction from the standard 4 cycles of chemotherapy used in previous COG trials. Patients with Stage I SCU, Stage II SCU, or any Stage III hepatoblastoma will be classified as intermediate-risk and will be treated with Regimen F (intermediate risk, stratum 3, has been closed to accrual as of 03/12/12). This treatment regimen is based on previous COG trials which administered 6 cycles of C5V therapy plus surgical resection of the tumor. However, to improve resection and survival rates, doxorubicin, an agent with proven efficacy will be added to the C5V therapy (C5VD). Surgical resection is necessary for cure and surgical resection whether by primary resection or orthotopic liver transplant (OLT) is intended after 4 cycles of intermediate-risk therapy. This trial will assess the feasibility in a cooperative group setting of timely referral (by the completion of Cycle 2) for OLT in children with hepatoblastoma designated as potentially unresectable following central surgical review and staging according to the PRETEXT (Pretreatment Extent of Disease) grouping system. AHEP0731 also aims to determine if PRETEXT grouping can predict tumor resectability and to assess if institutional assessment of PRETEXT grouping is reliable by comparing to PRETEXT grouping as performed by central review. All patients with any Stage IV hepatoblastoma as well as patients with any stage of hepatoblastoma and initial AFP <100 ng/mL will be classified as high-risk and will be treated with the novel combination of vincristine, irinotecan and temsirolimus in Regimen H in order to estimate the response rate of this new combination of agents. This regimen includes 2 cycles of “up-front” vincristine, irinotecan and temsirolimus in the initial 6 weeks of therapy. Patients who respond to vincristine/irinotecan/temsirolimus (VIT) will continue to receive this combination. Responding patients

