#### 1.2.4

To determine whether timely (between diagnosis and end of second cycle of chemotherapy) consultation with a treatment center with surgical expertise in major pediatric liver resection and transplant can be achieved in 70% of patients with potentially unresectable hepatoblastoma.

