#### Initial Treatment Plan for High-Risk Patients (Stratum 4): Regimen W

Initially, high-risk (Stratum 4) patients were treated on Regimen W. This regimen included 2 cycles of “up-front” VI window therapy. Patients who respond to VI were considered as responders. Responder patients then received a total of 6 cycles of C5VD therapy with 1 cycle of VI in between each 2-cycle block of C5VD. Non-responder patients only received 6 cycles of C5VD following the “up-front” window therapy.

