- 3 Tumor evaluation, ultrasound, echocardiogram (or MUGA), and audiogram may be done within 28 days prior to enrollment. It is highly recommended that patients have echocardiogram (or MUGA) and audiogram prior to treatment, but if patient is emergently treated (see [Section 3.2.2](#)) these may be deferred until clinically stable, but must be done before beginning Cycle 2.
- 4 A liver transplant consult should be performed as soon as possible after diagnosis but no later than first day of 3rd C5VD Cycle. (i.e. no later than first day of Cycle 5.) (See [Section 13.1.5](#)).
- 5 Tumor disease evaluation performed after VIT Cycle 2 for all patients and after Cycles 4, 6 & 8 for non-responders and after Cycles 4, 6 and 10 for responders until tumor removed. No scans required once all tumor has been removed or resolved until the end of therapy (see [Section 15.3](#)).
- 6 Pathology slides required for patients following all surgical (biopsy/resection) procedures (see [Section 14.0](#)).
- 7 Tumor tissue is strongly encouraged to be submitted and can be submitted if consent has been obtained and patient is enrolled on ABTR01B1 or other appropriate study (See protocol for details.)
- 8 See [Section 15.0](#) for details. Ultrasound only needs repeating if initial U/S showed tumor thrombus & does not need to be performed once thrombus has resolved or surgery performed.

9 PRETEXT/POST-TEXT grouping should be done by radiologist, surgeon and oncologist on all scans performed at diagnosis and pre-operatively as appropriate. (See [Section 10.2](#) and [Appendix I](#)).

10 The same modality is to be used each time for consistency.

11 Consent for PLUTO registry should be obtained within one month of liver transplant, see [Section 13.4](#).

12 If a biopsy is performed to make diagnosis, a repeat AFP should be obtained immediately prior to beginning chemotherapy (the same day).

13 The AFP obtained at the end of Cycle 2/prior to Cycle 3 must be recorded on the Reporting Period 1 CRF and submitted for central review assessment of response. If an AFP was obtained post Cycle 2, do not repeat prior to Cycle 3. Note: The Reporting Period 1 CRF must be submitted without delay, see the Data Submission Schedule for details.

**This table only includes evaluations necessary to answer the primary and secondary aims. Obtain other studies as required for good patient care.**

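### Primary aim 1.2.4 closes timely referral at the end of cycle 2, but Section 9.2 scores Regimen H and W patients as successes up to the third C5VD cycle, so for them the 16-of-25 count is more lenient than the aim

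*Combined protocol and SAP*

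**What the plan says.** Aim 1.2.4 asks whether "timely (between diagnosis and end of second cycle of chemotherapy) consultation with a treatment center" with the relevant surgical expertise can be reached in 70% of potentially unresectable patients. The Abstract uses the same window: "timely referral (by the completion of Cycle 2) for OLT in children with hepatoblastoma".

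Section 9.2, Hypothesis 2.0, gives two alternative routes to success. The first is that "the patient is enrolled on regimen F or regimen H and referred for transplant prior to the start of the third cycle of chemotherapy". The second is that "the patient is enrolled on regimen H or W and is referred for transplant by the start of the third cycle of C5VD". The rule then closes with "Otherwise the patient will be considered a referral failure". Because the routes are alternatives, the later deadline governs Regimen H.

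On Regimen H the third C5VD cycle is Cycle 5. Section 7.5, footnote 4, says so: "i.e. no later than first day of Cycle 5". For Regimen W, Section 4.1 records: "Responder patients then received a total of 6 cycles of C5VD therapy with 1 cycle of VI in between each 2-cycle block of C5VD". With two window cycles first, the third C5VD cycle for a W responder is Cycle 6.

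The paragraph just before the cutoff adds a further statement: "A patient for whom referral is considered appropriate who receives a consultation after enrollment will be considered a success with respect to feasibility". It gives no deadline. Referral is then declared successful if 16 or more of an expected 25 candidates are referred.

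**The concern.** A primary aim fixes one window, and the rule that decides the aim uses a longer one for some of the patients. A Stage IV patient first referred in Cycle 3 or 4 misses the aim but counts towards the 16.

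The decision has a use. Section 2.6 makes timely capture of at least 70% of eligible patients the precondition for a randomized transplant study, and a pass under Section 9.2 puts referral forward for possible inclusion in one. Following the plan as written, a report could state that referral by cycle 2 was shown feasible when only referral by a later date was.

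The undated sentence adds a smaller ambiguity. Taken literally, it would turn any late consultation into a success and contradict the failure clause shortly before it.

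**Working it through.** **1. The windows in days.** Cycles last 21 days (Section 4.6); assume no delays.
- Aim 1.2.4: end of Cycle 2 = 2 × 21 = Day 42.
- Regimen H: Cycle 5 Day 1 = 4 × 21 + 1 = Day 85. The delivery maps agree, placing Cycle 5 in Weeks 13-15.
- Regimen W responders, in the order VI, VI, C5VD, C5VD, VI, C5VD: Cycle 6 Day 1 = 5 × 21 + 1 = Day 106.

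**2. The plan's own table.** With X binomial (n = 25, p), P(X ≥ 16) is:

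| p | 0.50 | 0.55 | 0.60 | 0.65 | 0.70 | 0.75 |
|---|---|---|---|---|---|---|
| Recomputed | 0.115 | 0.242 | 0.425 | 0.630 | 0.811 | 0.929 |
| Section 9.2 | 11% | 24% | 42% | 63% | 81% | 93% |

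All six values reproduce. If everyone were scored on the cycle-2 window, p would be the rate in the aim.

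**3. What the mixed window does.** Let p be the true cycle-2 rate, taken as equal in all regimens. Let m of the 25 candidates be on H or W, and let s be the share of H/W patients not referred by cycle 2 who are referred before the third C5VD cycle. Then:
- Regimen F success rate = p
- H/W success rate q = p + (1 − p)s
- Pass chance = P(A + B ≥ 16), with A binomial (25 − m, p), B binomial (m, q), independent.

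Inputs for m: the INT-0098 breakdown in Section 9.2 has 10 Stage IV patients among 32, and 25 × 10/32 = 7.8, so 8. A lower alternative is the Stage IV share among its PRETEXT 3 candidates, 2 of 10, giving 25 × 2/10 = 5. Input for s: not in the documents; 10%, 25% and 50% are assumed.

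Worked case: p = 0.50, m = 8, s = 0.25 gives q = 0.50 + 0.50 × 0.25 = 0.625 and a pass chance of 0.210, against 0.115.

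| True cycle-2 rate | Table | m = 5; s = 10%, 25%, 50% | m = 8; s = 10%, 25%, 50% |
|---|---|---|---|
| 0.50 | 0.115 | 0.135, 0.170, 0.237 | 0.149, 0.210, 0.341 |
| 0.60 | 0.425 | 0.457, 0.507, 0.590 | 0.477, 0.557, 0.688 |
| 0.70 | 0.811 | 0.829, 0.854, 0.892 | 0.839, 0.877, 0.928 |

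**4. Direction.** Since s cannot be negative, q is never below p. For a given set of candidates, the longer window can add successes and never remove them.

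**The case against.** The strongest reply is that the later deadline is deliberate. It is stated in Sections 4.6, 7.5 and 13.1 and agrees with the delivery maps. Section 9.2 says before the cutoff what counts as success, and its table is headed by the probability of successful referral, not of referral by cycle 2. On this view only the aim and the Abstract were left behind. That stands as an account of how the mismatch probably arose. It does not remove it, because the primary aim still carries the earlier window.

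A second reply is that the aim's second cycle means the second C5VD cycle, which would bring the windows together. Section 13.1.3 does use the terms loosely. But Section 4.6 counts VIT cycles as chemotherapy (10 cycles: 6 C5VD plus 4 VIT), and the two success routes in Section 9.2 themselves distinguish the third chemotherapy cycle from the third C5VD cycle. This reading fails.

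Third, the effect is limited, and this stands. For Regimen F, which corresponds to 22 of the 32 historical candidates, the rule and the aim agree. A pass leads only to possible use in a later study; no patient's treatment or stopping decision depends on it.

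A reader might go further and infer that the 16-of-25 count does not measure the aim at all, that the table is wrong, or that the plan has no deadline. The documents support none of these. The count follows the aim for Regimen F, the table reproduces, and the sentence on consultation after enrollment follows directly on the dated rule and is probably shorthand for it.

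**Conclusion.** The inconsistency is in the text and needs no assumption: the aim and the Abstract close the window at the end of cycle 2, and Section 9.2 keeps it open to Cycle 5 on H and Cycle 6 for W responders. For those patients the count is more lenient than the aim, always in the direction of feasible.

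The size is illustrative. It rests on the historical stage mix carrying over, a common cycle-2 rate across regimens, independent patients and assumed late-referral shares. Across the scenarios shown, the pass chance is about 14% to 34% at a true cycle-2 rate of 50% (table 11%), 46% to 69% at 60% (table 42%), and 83% to 93% at 70% (table 81%). The rows below 70% matter most: there the aim is not met, and the longer window makes a pass likelier. At 70% the aim is met and the excess does little harm. If hardly any H/W patients were first referred between the two deadlines, the practical effect would be negligible.

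This should be corrected in the wording and the reporting. It is not a fault in the cutoff.

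**What to change.** - Reconcile aim 1.2.4 and the Abstract with Sections 4.6, 7.5, 9.2 and 13.1, and state which single window the feasibility count uses. Which deadline is right is for the study team to decide.
- Report the proportion of candidates meeting each window, overall and by regimen.
- Tie the sentence on consultation after enrollment to the dated rule, or delete it.

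The cost is wording plus a few reported proportions; the 16-of-25 cutoff and its table need no change. The study closed on July 20, 2018, so a window chosen now should be labelled post hoc unless the choice was recorded before the referral data were seen. Reporting both windows keeps the conclusion from resting on that choice. The case report forms are not among the documents, so it must be checked that consultation dates were collected. The downside is that the reported success rate may look less favourable.
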